8.1 Adverse Event Definitions

Adverse Event (AE): Any untoward medical occurrence, unintended disease or injury, or untoward clinical signs in subjects, users or other persons, deemed related to the investigational device (catheter and/or placement accessories), Neurapheresis procedure, or study required element (such as CSF sampling).

Serious Adverse Event (SAE): Adverse event as defined above that

- a) led to death,
- b) led to serious deterioration in the health of the subject, that either resulted in:
 - 1) a life-threatening illness or injury, or,
 - 2) a permanent impairment of a body structure or a body function, or
 - 3) in-patient or prolonged hospitalization, or
 - 4) medical or surgical intervention to prevent life-threatening illness or injury or permanent impairment to a body function,
- c) led to fetal distress, fetal death or a congenital abnormality or birth defect.

Unanticipated Adverse Device Effect (UADE): Any serious adverse effect on health or safety or any life-threatening problem or death caused by, or associated with, a device, if that effect, problem, or death was not previously identified in nature, severity, or degree of incidence in the investigational plan or application (including a supplementary plan or application), or any other unanticipated serious problem associated with a device that relates to the rights, safety, or welfare of subjects" (21 CFR§ 812.3(s)).

Unanticipated Adverse Device Effects (UADE) that occur in subjects enrolled in the clinical trial should be reported under the IDE program (812.150) to FDA and all reviewing institutional review boards (IRBs) and investigators within 10 working days after you first receive notice of the adverse effect(s).

8.2 Reportable Adverse Events

The table below outlines the protocol required reportable Adverse Events. Other events should also be reported if they are deemed by the investigator to be related to the investigational catheter, investigational system or Neurapheresis procedure, or study required element (such as CSF sampling).

Table 5: Reportable Adverse Events

Adverse Event	
Spinal headache with or without intervention	Systemic CNS infection/sepsis
Localized insertion site infection	Dural dissection
Meningitis	Paralysis
Brainstem herniation in the absence of re-bleed	Localized pain
Hematoma at insertion site	Peripheral neuropathy
Nausea/vomiting	Death

9. DEVIATIONS FROM THE PROTOCOL

An Investigator must not make any changes to or deviate from the protocol, except to protect the life and physical well-being of a subject in an emergency. An Investigator shall notify the Sponsor and the reviewing IRB of any deviation from the protocol to protect the life or physical well-being of a subject in an emergency, and those deviations which affect the scientific integrity of the clinical investigation. Such notice shall be given as soon as possible, but no later than 5 working days after the emergency occurred, or per prevailing local requirements, if sooner than 5 working days.

All deviations from the protocol, with the reason for the deviation and the date of occurrence, must be documented and reported to the Sponsor using the appropriate case report form. Sites are also required to report deviations to the IRB per local requirements.

Deviations will be reviewed and evaluated on an ongoing basis and, as necessary, appropriate corrective and preventive actions (including notification, center re-training, or discontinuation) will be put into place by the Sponsor.

9.1 Amendments to the Protocol

If a revision to the protocol is necessary which affects the rights, safety or welfare of the Subject or scientific integrity of the data, an amendment by the Sponsor is required. Appropriate approvals of the revised protocol must be obtained prior to implementation. Centers will be notified of any protocol amendment that is to be implemented. Communication from the Sponsor will apprise the center if an enrollment stop is required during the revision processes.

10. DATA ANALYSIS AND MANAGEMENT

The PILLAR-XT Study does not have a hypothesis based statistical endpoint due to the feasibility nature of the investigation. The following analysis populations and definitions will be used to analyze the PILLAR-XT data.

10.1 Analysis Populations

The following analysis populations will be used to perform the endpoint analyses.

Safety Population:

This population includes only subjects that were classified as Attempt to Treat or Treated Subjects and will be used to analyze all pre-defined safety endpoints.

Treated Population:

This population includes only subjects classified as Treated Subjects and will be used to analyze all pre-defined efficacy endpoints, including exploratory endpoints.

10.2 Endpoint Analysis Definitions

Enrollment will be stopped when 30 subjects have been enrolled and treated with Neurapheresis for at least 16 hours, however, this amount of therapy time is not considered a complete treatment as absolute blood clearance would not be expected. This study is expected to generate foundational data for development of the Neurapheresis treatment curve (e.g. time or volume needed to clear blood from the subarachnoid cisterns and lumbar spine).

Primary Endpoints:

1. Mean reduction of cisternal blood via CT post study therapy
 - a. Pre, 36 hour and post-Neurapheresis CTs will be evaluated by an independent neuroradiology core laboratory for quantification of blood volume. The core lab will utilize a three (3) member team for independent review of the primary endpoint with agreement of at least two (2) reviewers required.
 - b. Mean volumes will be compared using a paired t-test with an alpha level of .05. Pre blood volume will be compared to both the 36-hour and post-Neurapheresis blood volumes separately to support creation of the therapy curve. However, the Pre to Post Neurapheresis comparison will be the primary endpoint measure.
 - c. An analysis of variance may be considered based on results from exploratory sub-groups analyses
2. Proportion of subjects with Neurapheresis Catheter, System or Therapy related serious adverse events
 - a. Events will be reviewed by an independent medical monitor for relatedness and will be used to calculate this endpoint (Number of subjects with related SAEs/Number of subjects in the Safety Population)

Secondary Safety Endpoints:

- Proportion of subjects with successful catheter placement
 - This only includes the subjects in whom catheter placement was attempted (Number of subjects with catheter attempted/Number of subjects in the Safety Population)
- Proportion of subjects with device or study therapy related adverse events
 - Events will be reviewed by an independent medical monitor for relatedness and will be used to calculate this endpoint (Number of subjects with related AEs/Number of subjects in the Safety Population)
- Proportion of subjects with systemic CNS infection within 5 day of catheter removal
 - In order to be considered a CNS infection, the following must be true; abnormal growth was identified on CSF culture within 5 days of catheter removal, subject has physiologic symptoms of infection and treatment was administered specifically for that infection.
 - CNS infection events will be reviewed by an independent medical monitor for whether or not the event meets the criteria above and will be used to calculate this endpoint (Number of subjects meeting CNS infection definition/Number of subjects in the Safety Population)

Secondary Efficacy endpoints:

- Mean reduction of RBCs and total protein by CSF sample post study therapy
 - This calculation utilizes the pre-Neurapheresis sample (first CSF sample taken either at the time of needle insertion or after catheter placement, whichever laboratory value is greater) as compared to the post-Neurapheresis sample (last CSF sample taken prior to catheter removal)

- Mean length of Neuro ICU stay
 - Mean length of Neuro ICU stay will be calculated by two different methods, one using physical location change, the second using criteria for critical care monitoring.

Exploratory endpoints:

- Proportion of subjects requiring additional CSF management during study therapy or on-going CSF management post study therapy
- Reduction in biomarkers of inflammation as seen in CSF, blood and physiologic manifestations post study therapy
 - Such as cytokines, white blood cell counts, neutrophil/lymphocyte ratio, SIRS
- Proportion of subjects with symptomatic complications from aSAH
 - Such as hydrocephalus, clinical vasospasm and delayed cerebral ischemia
- Analysis of endpoints by the following sub-groups for any groups that have at least 5 subjects that meet the criteria for the group;
 - Age: <45, ≥45-<60, 60 – 70 years
 - Gender: male, female
 - Enrollment Modified Fischer grade: 2, 3, 4
 - Baseline cisternal Hijdra score: ≤15, 16-20, 21-25, 26-30
 - Neurapheresis time: <16hrs, ≥16-32hrs, >32-48hrs, >48hrs
 - Other sub-groups not yet defined

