5.7.1 Subject Enrollment Classifications

All patients who provide written consent to participate in the study will be considered enrolled study subjects, however not all subjects will contribute to the enrollment cap of N=30 Treated Subjects. Only treated subjects, as defined below, will contribute to the enrollment cap. As such, it is expected that up to 40 subjects may be enrolled to meet the enrollment cap. FDA, IRBs and Investigational sites will be notified when enrollment is complete.

Intent to Treat Subjects:

- Subjects who provide written informed consent but do not have placement of the study catheter attempted. This would include placement tools such as the epidural needle and guidewire. Intent to Treat subjects will be exited immediately. They will not count towards the enrollment cap of N=30 treated subjects. Only enrollment and study exit data will be collected in the study database.

Attempt to Treat Subjects:

- Subjects who provide written informed consent and have any portion of the catheter placement procedure attempted (including the epidural needle and guidewire) but placement was unsuccessful. Attempt to Treat subjects will be followed through 2 days post-attempt for safety then will be exited. They will not count towards the enrollment cap of N=30 treated subjects. They will be included in the analysis of safety endpoints but will not be included in the analysis of efficacy endpoints. Enrollment, catheter placement attempt, 2 day follow-up and study exit data will be collected along with any adverse events or protocol deviations if applicable.

Treated Subjects:

Subjects who provide written informed consent, have successful placement of the study catheter and had Neurapheresis initiated. These subjects will be followed out to 30 days according to the study protocol then exited. They will count towards the enrollment cap of

N=30 treated subjects and used in all analyses. All study data through the 30 day follow-up will be collected.

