7.2 Pre-Neurapheresis Imaging (CT) Requirements

As aneurysm securement (especially clipping) may change the amount of blood in the subarachnoid space, a CT is required following aneurysm securement but prior to beginning Neurapheresis. This CT will serve as the Baseline CT (pre-Neurapheresis CT) which, along with the screening CTs, will be compared to the post-Neurapheresis CTs. The Baseline CT is expected to be taken in a department scanner using optimal metal artifact reduction settings at the conclusion of aneurysm securement or following catheter insertion but prior to initiation of Neurapheresis therapy. The baseline CT must be reviewed to determine safety, via intracranial

stability, prior to beginning Neurapheresis therapy. In particular, the Investigator must assess the CT for the following criteria:

- no evidence of re-bleeding;
- no increasing mass effect;
- no effacement of the basilar cisterns;
- continued communication between the ventricles and subarachnoid space

In addition to the CT requirements above, study therapy cannot begin for at least 8 hours following aneurysm securement for subjects who underwent a clipping procedure.

If the subject meets these criteria, study therapy can be initiated. If the subject does not meet these criteria, either the subject can be exited, or another CT can be taken to determine baseline stability. If the subject still does not meet the safety criteria to begin study therapy after the second baseline CT, the subject is to be exited. If the study catheter was not placed prior to the baseline CT, the subject should be exited as an Intent to Treat Subject and no further follow-up is required. If however the study catheter was placed prior to the baseline CT, a 2-day follow-up is to be completed and the subject exited as an Attempt to Treat Subject.

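### The 5-day CNS infection rate is divided by subjects who have no catheter removal or who leave observation after a 2-day follow-up

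*Combined protocol and SAP*

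**What the plan says.** Section 10.2 lists "Proportion of subjects with systemic CNS infection within 5 day of catheter removal" as a secondary safety endpoint. A case needs abnormal growth on CSF culture inside that window, symptoms of infection, and treatment given for it. The formula is "Number of subjects meeting CNS infection definition/Number of subjects in the Safety Population". The primary safety endpoint uses the same denominator: "Number of subjects with related SAEs/Number of subjects in the Safety Population". So does the related-AE proportion.

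Section 10.1 forms the Safety Population from Attempt to Treat and Treated Subjects. Their follow-up differs:

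- **Attempt to Treat, failed placement** (Synopsis, 5.7.1): "Attempt to Treat subjects will be followed through 2 days post-attempt for safety then will be exited".
- **Attempt to Treat, catheter placed but baseline CT criteria not met** (7.2): "a 2-day follow-up is to be completed and the subject exited as an Attempt to Treat Subject".
- **Treated** (5.7.1): "These subjects will be followed out to 30 days according to the study protocol then exited".

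For the Attempt to Treat class, 5.7.1 limits the data: "Enrollment, catheter placement attempt, 2 day follow-up and study exit data will be collected along with any adverse events", plus deviations. There is no Neuro ICU discharge visit and no 30-day visit. Sections 7.6.1 and 7.6.2 have CSF cultures followed for 96 hours after the last sample, with reports that arrive after the 2-day visit submitted with the discharge data.

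**The concern.** An infection rate over a fixed window needs a denominator of subjects who entered the window and were watched to its end. Two kinds of Attempt to Treat subject do not meet that condition, for different reasons.

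A subject with a failed placement has no removal date. That subject cannot clearly satisfy the case definition but is always in the denominator.

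A subject whose catheter was placed but whose therapy never began did have an indwelling catheter and is at risk. Observation ends before the window does, and the plan has no scheduled route for a culture that turns positive after exit. Such an infection would be missing from the numerator while the subject stayed in the denominator.

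Sections 10.1 and 10.2 give no rule for incomplete follow-up, no common observation window and no separate line for Attempt to Treat subjects. The study aims to demonstrate safety further in about 30 people, so one event or a few denominator subjects visibly change the reported rate.

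**Working it through.** The documents give no sample-size or precision calculation for these proportions, so there is no planned figure to reproduce. The check compares the time windows and then sizes the effect on the rate.

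**Windows.** The infection window is 5 days from removal. Culture follow-up is 96 hours = 4 days from the last sample. Attempt to Treat observation is 2 days. If it runs from removal, it covers 2/5 = 40% of the infection window; if it runs from the attempt, it covers less. Section 7.2 does not say which. Even if the ±1 day visit window of 7.6.1 applies, the latest visit is day 3, still short of 4 and 5 days. For SAEs, 2 days is 2/30 = 7% of the Treated follow-up.

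**Number of Attempt to Treat subjects (a).** The documents do not give it. Section 2.1 reports 13 of 14 attempted placements successful in the earlier PILLAR study, so 30 successes need 30/(13/14) = 32.3 attempts, and a is about 2 to 3. Section 5.7.1 expects up to 40 enrolled for 30 treated, so the ceiling is a = 10. That ceiling requires no Intent to Treat subjects at all; they are among the 40 but outside the Safety Population.

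**Rate under the planned formula**, k/(30 + a), with exact (Clopper-Pearson) 95% upper limits for zero events:

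| a | Denominator | One event | Zero events, upper limit |
|---|---|---|---|
| 0 | 30 | 3.3% | 11.6% |
| 2 | 32 | 3.1% | 10.9% |
| 3 | 33 | 3.0% | 10.6% |
| 10 | 40 | 2.5% | 8.8% |

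The loss for one event is 3.33 − 3.13 = 0.2 points at a = 2, and 3.33 − 2.50 = 0.8 points at the ceiling. The plan specifies no confidence intervals here; the limits are added to show scale.

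**The two groups act differently.** Failed placements only enlarge the denominator. Subjects placed but not started belong in the denominator; their problem is missed events. If both of 2 Attempt to Treat subjects were of this kind, and no infection was seen, the true proportion could lie anywhere from 0/32 to 2/32 = 6.3%. The upper end is a bound, not an expectation.

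**Related SAEs.** Attempted subjects can contribute events. With one attempt-related SAE and none in Treated Subjects, the planned formula gives 1/32 = 3.1%, while a Treated-only proportion gives 0/30 = 0%.

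**The case against.** Several points on the other side have force.

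- Including attempted subjects in a safety population is sound, since needle and guidewire are exposure. This stands, and it is why the SAE and AE denominators should not be narrowed.
- Comparing 1/32 with 1/30 shows a change of denominator. It does not estimate unseen infections, and no input for that exists. This stands too.
- In the earlier study, all 13 subjects with a placed catheter went on to therapy, so the group with the clearest gap numbered zero there. The corresponding number for PILLAR-XT is not given. The group may be very small, but 7.2 provides for it explicitly.
- No planned decision turns on the rate. The study "does not have a hypothesis based statistical endpoint due to the feasibility nature of the investigation", and the enrollment-hold rules in 13.3 count events and do not list infection. This limits the consequences; it does not make the rate interpretable.
- Table 6 (13.4.2) requires AE reporting through the 30-day follow-up and SAE reporting to the end of the study. An Attempt to Treat subject has already exited by then and has no 30-day visit, so this does not close the gap.

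A reader might infer that every safety proportion in 10.2 is biased in the device's favour. The documents do not support that. Attempt-related SAEs and AEs enter the numerator and can raise the pooled figure, and the SAE endpoint states no time window that early exit would cut short. For SAEs and AEs, the supportable statement is that one figure mixes unequal observation.

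**Conclusion.** The point holds for the CNS infection endpoint. As written, its formula counts as event-free some subjects for whom the window is undefined and others not observed to its end. The likely effect is small: about 0.2 percentage points for one infection, and a zero-event upper limit of 10.9% instead of 11.6%. This assumes 30 Treated Subjects and 2 Attempt to Treat subjects at the earlier placement rate. The ceiling is 2.5% against 3.3%. The Treated count could slightly exceed 30, because 10.2 stops enrollment at 30 subjects with at least 16 hours of therapy; that does not alter the conclusion.

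For the related-SAE and related-AE proportions the finding is narrower: the denominator is defensible, but the pooled figure needs a breakdown to be read correctly. The change is worth making because it is cheap and one of these proportions is a primary endpoint.

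**What to change.** 1. In 10.1 and 10.2, define the CNS infection denominator as subjects in whom a study catheter was placed and removed, with infection status ascertained through 5 days after removal. Include those whose therapy was never started.
2. Reconcile the 2-day exit wording in the Synopsis, 5.7.1 and 7.2 with a day-5 chart and culture check for subjects placed but not started. State whether their 2-day follow-up runs from the attempt or from removal. Align the class definition as well: the Synopsis and 5.7.1 describe only unsuccessful placement, while 7.2 adds successful placement without therapy.
3. Report any infection after a failed placement separately.
4. Keep the Safety Population as the main denominator for related SAEs and related AEs, so that attempt-related events still count. Add a breakdown: Treated Subjects through day 30, and Attempt to Treat subjects through their own follow-up, with days observed.

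The cost is small wording changes in several sections, possibly a line in Table 4, and a chart review in a few subjects. Section 7.6.2 expects Neuro ICU discharge on average 10 to 14 days after aneurysm securement, so most should still be in the unit at that check.

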5.3 Institutional Standard of Care Treatment

The PILLAR-XT study does not require a uniform method for the treatment to secure the aneurysm i.e., Clip vs. Coil. Additionally, the Investigator may use accepted institutional SOC and professional discretion for interventions and treatments which include, but are not limited to:

- SOC neurological assessments
- SOC imaging
- ICP monitoring
- EVD placement
- “Triple H” therapy (hypertension, hypervolemia, hemodilution)

- Hyperventilation
- Nimodipine
- Seizure prophylaxis
- Antimicrobial prophylaxis

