7.5.7 CSF Sampling During Neurapheresis

During catheter in-dwelling and Neurapheresis therapy, CSF samples will be obtained at regular intervals until the catheter is removed. A maximum of 11 CSF samples total per subject will be taken. Ten of those during catheter indwelling, though fewer may be taken if the catheter must be removed early.

Samples will be taken according to the schedule in Table 10 below. The initial CSF sample will be taken during catheter placement however, the first sample taken during catheter in-dwelling will be considered the Baseline CSF sample (pre-Neurapheresis sample) to which the later samples will be compared. The last CSF sample taken will be considered the Final sample or (post-Neurapheresis sample) which will be compared to the Baseline sample for applicable endpoint analyses. To account for different assay requirements, CSF sample volumes are different for the initial and seventh (40 hr) sample than those in between.

It is allowable to collect less CSF sample volume for completion of the Cell counts with Differentials based on site specific laboratory requirements. Current laboratory certificates are

required by the sponsor with laboratory processes to be made available upon request. Care should be taken to ensure laboratory samples are handled and processed consistently for accurate data reporting.

During catheter in-dwelling, the first sample (#2 on Table 10 below) should be taken after 1 hour ($\pm 30\text{min}$) of Neurapheresis therapy. The MNeuro CFS will assist in monitoring the therapy time in order to prepare for the sample. The next CSF sample should be taken at 8 hours ($\pm 2\text{hr}$) from catheter securement (8 hours of catheter in-dwelling) then each subsequent sample taken every 8 hours ($\pm 1\text{hr}$) from the previous scheduled sample (i.e. every 8 hours during catheter in-dwelling).

Table 3: Required CSF Samples

Sample #	Sample Metric	Required Assay	CSF Sample Volume
1	During Catheter Placement (needle stick)	Cell counts with Differential: RBC, WBC, neutrophils, lymphocytes, etc. Chemistries: Total protein, Glucose, Culture	3ml
		CSF Biomarkers (requires -80° storage until shipped) ^β	2ml ^β
2	1hr ($\pm 30\text{min}$) of Neurapheresis	Cell counts with Differential and Chemistries	3ml
3	8hr ($\pm 2\text{hr}$)*	Cell counts with Differential and Chemistries	3ml
4	16hr ($\pm 2\text{hr}$)*	Cell counts with Differential and Chemistries	3ml

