5	24hr ($\pm 2\text{hr}$)*	Cell counts with Differential and Chemistries	3ml
6	32hr ($\pm 2\text{hr}$)*	Cell counts with Differential and Chemistries	3ml
7	40hr ($\pm 2\text{hr}$)*	Cell counts with Differential and Chemistries	3ml
		CSF Biomarkers (requires -80° storage until shipped)	2ml
8	48hr ($\pm 2\text{hr}$)*	Cell counts with Differential and Chemistries	3ml
9	56hr ($\pm 2\text{hr}$)*	Cell counts with Differential and Chemistries	3ml
10	64hr ($\pm 2\text{hr}$)*	Cell counts with Differential and Chemistries	3ml
11	72hr ($\pm 2\text{hr}$)* ^γ	Cell counts with Differential and Chemistries	3ml

*time measured from catheter securement (beginning of indwelling time)

^βif a CSF sample for biomarkers was not obtained during catheter placement (sample #1), it can be done with sample #2

^γif the catheter is removed prior to reaching the 72hr indwelling limit, a final CSF sample should be taken just prior to catheter removal

Center personnel shall work with the MNeuro CFS to time the CSF sampling as to not interfere with SOC patient care. To ensure sample consistency and minimize subject impact, samples are to be taken using the automated sampling process within the system. The system is switched to “sample mode” then using sterile technique, a syringe is inserted into the three-way sample stopcock. Sample mode should be set at the nominal flow rate of 0.5ml/minute. The system will automatically fill the syringe. Once the appropriate amount of CSF has been retrieved, sample

mode can be stopped and the syringe removed. The MNeuro CFS will pause the system prior to the sample acquisition, and will leave the system paused for a short period post sampling e.g., approx. 15 min, to allow for the CSF fluid balance to recover.

Also reference the IFU for additional details in regard to CSF sampling. A de-identified laboratory print-out of the required CSF assay analyses must be provided to the Sponsor. The original laboratory results must be available for monitoring.

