Data Items	Screening / Enrollment	Catheter Placement	Neurapheresis Procedure	2-Day Post-Neurapheresis (± 1 -day)	Discharge from Neuro ICU	30 Days Post-Neurapheresis (± 3 days)
Demographics, Medical Hx, SAH Symptomology	✓					
Aneurysm data; location, measurements, securement, etc.	✓					
Modified Fisher Grade	✓					
WFNS	✓					
Hunt & Hess	✓					
Glasgow Coma Scale (GCS)	✓		✓ [‡]	✓	✓	
Peripheral Check			✓ [‡]			
Glasgow Outcome Scale Extended (GOSE)						✓
Modified Rankin Scale (mRS)					✓	✓
Barthel Index						✓
Montreal Cognitive Assessment (MoCA)						✓
Activated Clotting Time Data (if applicable)		✓				
Catheter/System data		✓	✓			
CSF Sampling and Laboratory Reports		✓	✓	✓ ^β	✓ ^β	
CBC with Differential/CMP Blood Test and Laboratory Reports	✓		✓**	✓		
Protocol Required CTs Scans		✓*	✓***	✓		
SOC CT Scans	✓		✓	✓	✓	
Fluoroscopy or X-ray Image of Catheter		✓	✓ [©]			
ICP Data (if applicable)			✓ [‡]	✓	✓	
Clinical and Hospital Data e.g., LOS, location, vital signs, complications	✓		✓	✓	✓	✓
Protocol Deviations	✓	✓	✓	✓	✓	✓
Adverse Events		✓	✓	✓	✓	✓

* CT is required after aneurysm securement but prior to Neurapheresis initiation and must be assessed to ensure intracranial stability prior to beginning therapy

** Blood sample is required at 36 hrs (± 4 hr) and at the end of catheter indwelling or 72 hours (± 4 hr) whichever is earlier

*** CT is required at 36 hrs (± 4 hr) and at the end of catheter indwelling or 72 hours (± 4 hr) whichever is earlier [cannot be bedside CT]

† ICP (for subjects with EVD), Lumbar Pressure GCS and peripheral checks are required every 1 hours (± 1 hr) during catheter in-dwelling

‡ Reports for CSF cultures should be followed through 96 hours from the last sample taken prior to catheter removal

© Catheter image to document final catheter placement post-Neurapheresis therapy

8. ADVERSE EVENTS (AEs)

The Study will not track all-cause AEs or AEs related to SOC or the SAH clinical pathway e.g., re-bleed, deep vein thrombosis, skin breakdown etc. Study required event reporting is limited to AEs directly related to the investigational catheter, investigational system or Neurapheresis procedure, or study required element (such as CSF sampling). In cases where the event may have an attributable dual causality i.e., SAH clinical path or the Neurapheresis procedure, the center should report the event.

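### The CNS infection endpoint runs to 5 days from catheter removal, but no rule clearly collects CSF cultures drawn after removal, so later infection may be under-ascertained and treated culture-negative meningitis cannot count

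*Combined protocol and SAP*

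**What the plan says.** Section 10.2 makes three conditions jointly necessary. It opens with "In order to be considered a CNS infection, the following must be true" and then lists "abnormal growth was identified on CSF culture within 5 days of catheter removal, subject has physiologic symptoms of infection and treatment was administered" for that infection in particular. Relatedness to the device is not a condition. The medical monitor checks events against these criteria, and the denominator is the Safety Population (Attempt to Treat plus Treated Subjects).

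The sources of culture data are these:

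- **Sampling.** Section 7.5.7 says "CSF samples will be obtained at regular intervals until the catheter is removed" and "A maximum of 11 CSF samples total per subject will be taken". Table 3 includes culture in the panel ("Chemistries: Total protein, Glucose, Culture"). On early removal, "a final CSF sample should be taken just prior to catheter removal".
- **Culture read-out.** The footnote to Table 4 says "Reports for CSF cultures should be followed through 96 hours from the last sample taken prior to catheter removal". Sections 7.6.1 and 7.6.2 tie the CSF reports they expect to that same 96 hours.
- **Later visits.** The 2-day, Neuro ICU discharge and 30-day visits require no new CSF sample.
- **Adverse events.** Section 8 restricts reporting to events related to the catheter, system, procedure or a study-required element, and asks for events of possible dual cause. Table 5 lists meningitis and systemic CNS infection/sepsis as separate entries, with no culture condition.
- **Background care.** Section 5.3 leaves "Antimicrobial prophylaxis" to institutional practice.

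**The concern.** The endpoint and its data sources do not have the same scope. The endpoint covers CNS infection of any cause to 5 days. The required cultures stop at removal, and the adverse event route admits only events thought related to the study. An infection that declares itself after removal is counted only if the treating team happens to culture CSF and the result reaches the sponsor, and the plan does not clearly require the second step. A subject with no later culture and a subject with a negative later culture look the same in the numerator.

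The culture condition also leaves out a subject who is diagnosed with and treated for meningitis without growth. The documents do not say how often that happens, but they allow antimicrobial prophylaxis.

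At stake is how a low rate will be read. Infection is a listed device risk (Table 2). The in-dwelling limit rises from 36 hours in PILLAR to 72 hours here. Section 2.1 lists the absence of CNS infection and culture growth in PILLAR among its safety findings, so a rate near zero in this study would probably be read the same way.

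**Working it through.** **1. The sampling schedule (Table 3).** One needle-stick sample, one at 1 hour of therapy, and 72/8 = 9 eight-hourly samples give 1 + 1 + 9 = 11, of which 10 are in-dwelling. This reproduces the stated maximum. None is scheduled after removal.

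**2. The window against the read-out.** The window is 5 × 24 = 120 h.

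- Last sample at removal: read-out ends 96 h after removal.
- Widest allowed timing (sample at 70 h, removal at 76 h): 70 + 96 − 76 = 90 h after removal.

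Both fall inside 120 h. Section 10.2 dates a case by when growth was identified, so a required culture can satisfy the definition.

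**3. Routes into the numerator for infection starting after the last required sample.**

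- *Required culture:* none.
- *Standard-of-care culture:* the definition does not exclude it. However, Sections 7.6.1 and 7.6.2 explicitly request standard-of-care imaging, while their CSF text concerns the earlier cultures. The 2-day visit's general request for laboratory and standard-of-care source documents does not reach day 5.
- *Adverse event report:* open if the event is judged related or possibly of dual cause. An infection attributed solely to the ventricular drain (required by Section 7.5.4) is outside the stated scope.

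**4. Culture-negative meningitis.** It fails the first of three necessary conditions and cannot count here. If adjudicated as related, it counts in the related adverse event endpoint and, if serious, in primary endpoint 2. There it is pooled with other related events.

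**5. Attempt to Treat Subjects.** They are in the denominator but exit at 2 days (Section 5.7.1). Those with failed placement may have no removal to start the 5-day clock. With 30 Treated Subjects and an assumed Safety Population of 35, one event is 1/30 = 3.3% or 1/35 = 2.9%.

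**6. Size, by assumption only.** Let c be the culture-negative share of infections, l the share starting after the last required sample, and s the share of those late cases cultured under standard care with the result collected. Then observed rate = true rate × (1 − c) × [(1 − l) + l × s]. With an assumed true rate of 5% and 30 subjects:

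| c | l | s | Observed rate | P(0 of 30) |
|---|---|---|---|---|
| 0 | 0.6 | 1 | 5.0% | 21.5% |
| 0.1 | 0.3 | 1 | 4.5% | 25% |
| 0.3 | 0.3 | 0.5 | 3.0% | 40% |
| 0.5 | 0.6 | 0 | 1.0% | 74% |

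None of c, l, s or the true rate is in the documents. The first row shows no loss at all. For scale, 0 of 30 has a 95% Clopper-Pearson upper limit of 11.6%.

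**The case against.** A reader might infer from 96 h against 120 h that the endpoint contradicts its own schedule. The documents do not support that. Growth is dated by identification, the read-out ends inside the window, and Section 2.1 describes 96 hours as standard testing. Nothing suggests that a culture negative at 96 h would yield more on day 5. The uncovered 24 to 30 h is clock time, not a measure of missed cases.

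The rest of the opposing case is also substantial:

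- Standard-of-care cultures can count. Subjects are inpatients under close observation, with Neuro ICU discharge expected on average 10–14 days after securement. Records are reviewed for adverse events at each visit, and the medical monitor receives available source documents.
- Meningitis is a named reportable event, and Section 8.2 could be read as making every Table 5 event reportable whatever its cause.
- With up to 11 cultures per subject, requiring growth, symptoms and specific treatment is a reasonable guard against contaminants.
- The endpoint is secondary and descriptive, with no threshold, and CNS infection is not among the enrolment-hold events in Section 13.3.

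These points justify keeping the strict definition and limit the consequence. They do not close the gap. That a culture may count is different from its being collected. Section 8.1 defines an adverse event as one deemed related, so the broad reading of Table 5 is uncertain. The related-event endpoints cannot stand in for an endpoint with no relatedness condition.

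**Conclusion.** The point holds as a gap in ascertainment. The endpoint has a wider scope, in time and in cause, than the data the plan clearly requires, so infection arising after removal may be under-counted. Treated culture-negative meningitis is outside this endpoint but not lost to the trial if judged related.

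A reader might go further and call the rate biased low. Under-ascertainment of clinical infection is the likelier direction, but the documents show neither its size nor the net direction. If every infection is culture-positive and every late one is cultured and submitted, there is no shortfall. Because abnormal growth is undefined and cultures are repeated, some false positives are possible, though the symptom and treatment conditions limit them.

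One case is 1/30 = 3.3 percentage points in 30 subjects. It would be 1/40 = 2.5 points in 40, but 40 is expected total enrolment including Intent to Treat Subjects, so the Safety Population should be smaller. This is a cheap improvement to a descriptive secondary endpoint and does not threaten the trial's main conclusions.

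**What to change.** 1. Keep the three-part definition and the 96-hour culture read-out.
2. State in Section 10.2 that standard-of-care CSF cultures count. In Section 7.6 and Table 4, require submission of any obtained through day 5 after removal, whatever the attributed cause.
3. Beside the strict rate, report the number of subjects with any CNS infection, including meningitis, diagnosed and treated through day 5 regardless of culture result, as reviewed by the medical monitor.
4. Because Attempt to Treat Subjects exit at 2 days, also report the rate among Treated Subjects.

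The changes are to case report form and analysis wording. They need no new samples and do not alter care, since only existing hospital results are collected. The costs are slight extra data collection and a possibly less favourable reported rate.
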